Suppose p_1 , p_2 , p_3 , and p_4 are ARIA-E rates at Week 24 in the standard dosing arm, the dosing skipping arm, the titration arm and the Cmax arm, respectively. There are 3 parameters associated with the primary objective of Study AACQ: 1) the relative risk reduction in ARIA-E in the 2nd treatment arm (dose skipping regimen) versus the 1st treatment arm (standard dosing regimen) at Week 24, denoted by $RD_{21} = \frac{p_1 - p_2}{p_1} = 1 - \frac{p_2}{p_1}$, where $\frac{p_2}{p_1}$ represents a relative risk between the 2nd treatment arm and 1st treatment arm. A positive relative risk reduction means the relative risk is smaller than 1; 2) the relative risk reduction in ARIA-E in the 3nd treatment arm (titration regimen) versus the 1st treatment arm at Week 24, denoted by $RD_{31} = 1 - \frac{p_3}{p_1}$, where $\frac{p_3}{p_1}$ represents a relative risk between the 3rd treatment arm and 1st treatment arm; 3) the relative risk reduction in ARIA-E in the 4th treatment arm (Cmax regimen) versus the 1st treatment arm at Week 24, denoted by $RD_{41} = 1 - \frac{p_4}{p_1}$, where $\frac{p_4}{p_1}$ represents a relative risk between the 4th treatment arm and 1st treatment arm.

A relative risk reduction in ARIA-E greater than 0 (which implies relative risk smaller than 1) favors alternative treatment arm. The posterior probability of obtaining at least 20% relative risk reduction of ARIA-E comparing the alternative dosing regimen versus the standard dosing regimen by Week 24 is considered as a positive primary outcome. Bayesian logistic regression will yield 3 posterior distributions of RD_{21} , RD_{31} , and RD_{41} . Afterwards, following 3 posterior probabilities will be derived:

$$Pr(RD_{21} \ge 0.2 \mid 24$$
-week ARIA-E data); (1)

$$Pr(RD_{31} \ge 0.2 \mid 24\text{-week ARIA-E data});$$
 (2)

$$Pr(RD_{41} \ge 0.2 \mid 24\text{-week ARIA-E data}).$$
 (3)

Conditional on 24-week ARIA-E data, the computed posterior probability from (1), (2), or (3) will evaluate how likely it is to achieve at least 20% relative risk reduction in ARIA-E comparing the alternative treatment arm with the standard one. A posterior probability >80% will lead to a conclusion that at least 1 alternative dosing regimen reduces ARIA-E risk by at least 20% compared to standard dosing regimen.

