4.3.2. Main analytical approach

The number of ARIA-E events and the percentage of participants by treatment arm with any occurrence of ARIA-E events will be tabulated. The percentage of any occurrence of ARIA-E events is equivalent to ARIA-E incidence proportion. The primary analysis will use a Bayesian logistic regression model to estimate relative risk reduction in ARIA-E between alternative donanemab dosing regimen and standard donanemab dosing regimen given ARIA-E data up to Week 24.

The logistic regression model will include categorical effects of treatment arm, APOE e4 genotype, baseline presence of microhemorrhage, baseline presence of superficial siderosis, and baseline amyloid level. Treatment arm is a multinomial variable with 4 levels. APOE e4 genotype status has 3 levels: heterozygous carrier, homozygous carrier, and non-carrier. As participants with ≤4 microhemorrhages at baseline are eligible to enroll into this study, the model needs to adjust for baseline presence of microhemorrhage which is a binary predictor. The proposed model will also assess the impact of baseline presence of superficial siderosis because the study allows enrollment of eligible subjects with 1 area of cortical superficial siderosis. Baseline amyloid values are divided into terciles.

An integral part of Bayesian analysis is the formulation of prior distributions for regression coefficients. A diffuse prior will be assigned to all slope parameters to reflect the impact of the alternative dose regime and the effect of baseline covariates solely based on the data collected from the study. For the intercept parameter, a mixture prior will be using information on ARIA-E rates of the standard donanemab dosing regimen by 24 weeks from AACI – Addendum 9 study. The mixture prior will have a diffuse and an informative component. However, the informative component will have much less variability than the diffuse component. Both prior means are equal to log odds of the ARIA-E incidence in AACI-Addendum 9 study at Week 24. One normal prior has much less variability compared to another normal prior that is relatively flat. 50% weight will be assigned to each component of the mixture a priori.

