Through an iterative MCMC (Markov chain Monte Carlo) sampling method, a posterior distribution of ARIA-E incidence in Arm 1 (p_1) , Arm 2 (p_2) , Arm 3 (p_2) , or Arm 4 (p_4) at Week 24 will be simulated knowing the likelihood function of the logistic regression and prior density of individual regression coefficient. Afterwards, a posterior distribution of relative risk reduction in ARIA-E such as RD_{21} , RD_{31} , or RD_{41} as defined in Section 2 will be generated as well.

Posterior summary statistics, like posterior mean, posterior median, 2-sided equal-tailed 95% of posterior interval of RD_{21} , RD_{31} , or RD_{41} may be reported. The posterior probability of RD_{21} , RD_{31} , or RD_{41} being no smaller than 20% will be presented as well. The Bayesian logistic regression model can be implemented via both MCMC procedure in SAS and rjags package in R.

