4.3.3. Sensitivity Analyses

One type of sensitivity analysis that will be conducted is to assess how a posterior probability described in (1), (2), or (3) in Section 2 will be changed if the margin or threshold is changed for relative risk reduction in ARIA-E. The calculated posterior probability regarding effect of interests will be computed.

One such analysis will be to compute a posterior probability of RD_{21} , RD_{31} , or RD_{41} being greater than 0. This is analogous to testing any positive relative risk reduction when a frequentist logistic regression was applied. Suppose from a posterior distribution of RD_{21} ,

$$Pr(RD_{21} > 0 \mid 24$$
-week ARIA-E data) > 0.8,

the conclusion would be compared to the standard dosing arm, the dosing skip arm had a significant positive relative risk reduction of ARIA-E.

Another type of sensitivity analysis will be to test how robust the yielded posterior probabilities will be if a neutral prior is assigned to the intercept coefficient rather than the mixture prior stated in Section 4.3.2.

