4.4. Secondary Endpoints Analysis

4.4.1. 12-month and 18-month incidence of ARIA-E

For the analysis of 52-week ARIA-E incidence, all 4 scheduled MRIs (weeks 4, 12, 24, 52) and unscheduled MRI data as well as treatment-emergent cluster data will be used first to obtain descriptive statistics including total number and proportion of patients with ARIA-E in 1-year in AACQ and by treatment arm.

Like the method for analyzing the primary endpoint, a Bayesian logistic regression will be applied before answering whether relative risk reduction of ARIA-E in 52 weeks is significant comparing the dosing skip arm with standard dosing arm, or comparing the titration arm with standard dosing arm, or comparing the Cmax arm with standard dosing arm. A diffuse prior will be used for each slope parameter in this Bayesian logistic regression model and a mixture prior for the intercept parameter will be elicited from 52-Week ARIA-E outcome in AACI-Addendum 9 study. The probability that one alternative dosing arm has a minimum of 20% risk reduction in ARIA-E in one year compared to the standard dosing arm will be derived from each of 3 simulated posterior distributions in relative risk reductions. In addition, the sensitivity analyses proposed in Section 4.3.3 will be used for 52-week analysis of ARIA-E.

All scheduled postbaseline MRIs (weeks 4, 12, 24, 52, and ED) and unscheduled MRI data as well as treatment-emergent cluster data will be analyzed for ARIA-E events up to Week 76 using the framework in Section 4.3.2 or following the descriptions for the analysis of 1-year incidence of ARIA-E.

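### The historical prior is set on the intercept of a four-covariate model with no stated coding, and the reported power and false-positive rate come from a model that lists no covariates

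*SAP*

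**What the plan says.** SAP 4.3.2 defines the primary model: "The logistic regression model will include categorical effects of treatment arm, APOE e4 genotype, baseline presence of microhemorrhage", then baseline siderosis and baseline amyloid in terciles. It lists the genotype levels ("APOE e4 genotype status has 3 levels: heterozygous carrier, homozygous carrier, and non-carrier") but names no reference level, contrast or centring for any covariate. Slopes get diffuse priors. The intercept gets a 50/50 mixture of two normals: "Both prior means are equal to log odds of the ARIA-E incidence in AACI-Addendum 9 study at Week 24". Their spread is described only in words: "One normal prior has much less variability compared to another normal prior that is relatively flat".

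SAP 5 gives numbers. The arm slopes have N(0, 4) and the intercept has 0.5 x N(-1.48, 4) + 0.5 x N(-1.48, 30.19). The second argument is not labelled as a variance or a precision. No covariate term is listed. From that model SAP 5 reports success in 927 of 1,000 simulated trials and a 5% one-sided false-positive rate.

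Protocol 9.3.2 says the amount of borrowing depends on how similar the standard regimen's Week 24 ARIA-E rate is to the historical rate. SAP 2 defines p1 as an arm-level quantity ("ARIA-E rates at Week 24 in the standard dosing arm"). SAP 4.3.3 plans a check "if a neutral prior is assigned to the intercept coefficient rather than the mixture prior stated in Section 4.3.2", and Protocol 9.3.2 plans an analysis of this study's data alone.

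**The concern.** With reference-cell coding, the intercept is the standard-arm log odds for one combination of genotype, microhemorrhage, siderosis and tercile. Protocol 2.2 says APOE e4 carriers have higher ARIA-E risk, so that log odds differs between cells and in general is not the overall value of -1.48. The mixture then judges agreement between history and trial by comparing a cell with an average, which is not the comparison Protocol 9.3.2 describes. A low-risk reference cell is pulled upward, which raises the fitted standard-arm rate and favours the alternative arms. A high-risk cell is pulled the other way.

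Two things are at stake. First, the primary success rule (posterior probability above 0.8 of at least a 20% relative reduction, in any alternative arm) could turn on a programming default. SAP 4.3.2 allows two packages: "The Bayesian logistic regression model can be implemented via both MCMC procedure in SAS and rjags package in R". Second, the 92.7% and 5% figures are not shown for the model that will be fitted. The construction is reused at Week 52 (SAP 4.4.1: "a mixture prior for the intercept parameter will be elicited from 52-Week ARIA-E outcome in AACI-Addendum 9 study") and for ARIA-H (SAP 4.4.3).

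**Working it through.** **Step 1: the prior.** ln(0.185/0.815) = -1.48, so the prior mean is the overall Addendum 9 log odds.

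**Step 2: reproduce SAP 5.** Treatment-only model, 180 per arm (720/4), 18.5% against 11.1% for power, 18.5% in all arms for false positives (FPR).

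| Reading of N(., .) | Power | FPR |
|---|---|---|
| A: 30.19 a precision, both 4s variances | 93.0% | 5.8% |
| B: both mixture terms precisions, slope variance 4 | 92.2% | 6.2% |
| All variances | 84.9% | 8.4% |
| All precisions | 74.8% | 2.1% |

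The exact 95% interval for 927/1000 is 90.9% to 94.2%, so only A and B fit. Two further facts favour a precision:

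- 30.19/(0.185 x 0.815) = 200, the information in about 200 participants at 18.5%.
- A precision of 30.19 is an SD of 0.182, so the informative component's 95% range is -1.48 ± 1.96 x 0.182, or 13.7% to 24.5%. If that component instead had variance 4, the range would be 0.4% to 92%.

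**Step 3: assumed covariate effects.** The documents give none, so these are illustrations.

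- Mix: non-carrier/heterozygote/homozygote 30/50/20%, microhemorrhage 15%, siderosis 5%, equal terciles.
- Odds ratios (weak/moderate/strong): APOE per step 1.5/2/3; tercile per step 1.2/1.3/1.5; microhemorrhage and siderosis 1.3/1.5/2 each.
- The standard arm is calibrated to 18.5% overall.

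The low-risk cell (non-carrier, lowest tercile, no microhemorrhage or siderosis) then has a rate of 10.7/7.3/3.8%. Moderate case for homozygote, top tercile: odds 0.073/0.927 = 0.079; 0.079 x 2² x 1.3² = 0.53, a rate of 35% (weak 28%, strong 44%). Both are compared with a prior centred on 18.5%.

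**Step 4: fit the SAP 4.3.2 model under reading A.** The SAP 5 prior values are carried over, and all slopes are N(0, variance 4). Risks are standardised over all 720 participants. There are 3,000 trials per setting, with the same data under each reference (Monte Carlo SE 0.4 to 0.9 point). Entries are weak/moderate/strong.

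| Reference cell | FPR % | Power % |
|---|---|---|
| Non-carrier, lowest tercile | 13.0/11.1/7.0 | 90/87/88 |
| Heterozygote, lowest tercile (first-listed genotype) | 9.7/12.2/12.7 | – |
| Non-carrier, top tercile (last-listed genotype) | 10.1/12.9/11.1 | – |
| Heterozygote, middle tercile | 7.2/8.2/9.7 | – |
| Homozygote, top tercile | 4.4 to 5.9 | 78.5/76.5/80.3 |
| All four covariates high | – | 81 to 82 |
| No borrowing | 7.8/7.7/6.5 | 85 to 86 |

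A dash means the figure is not reported here. Between the low-risk and the homozygote/top-tercile reference, on identical data, the success decision changes in 11.4/10.9/7.4% of trials with a true 40% reduction and in 8.7/5.3/1.1% of null trials.

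Under reading B the spread is wider: low-risk FPR 14.6/17.9/20.6%, homozygote/top-tercile power 78.2/73.0/67.5%. If both mixture terms are variances it almost disappears: power 84 to 87%, FPR 5.8 to 7.8%, and 0.4 to 1.7% of decisions change.

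**Step 5: other assumptions.** A second simulation under reading A used other odds ratios (weak set: APOE 1.5 and 2.5; moderate set: 2 and 5). The low-risk FPR was 13.9% (weak) and 8.3% (moderate). With a homozygote reference and other covariates low it was 4.6% and 4.8%. Its lowest power was 81.6%, with all covariates high; it did not run the homozygote/top-tercile cell. A further run of that cell gave power of 80.2% (weak) and 78.4% (moderate).

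**The case against.** The harm needs three things together: reference-cell coding, 30.19 read as a precision, and covariate effects that the documents do not state. That is correct. What is certain is narrower: an unstated coding, an unlabelled prior parameter, and reported operating characteristics for a model with no listed covariates.

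Power below 80% under reading A occurs at one extreme reference cell, at two of three assumed strengths and by a small margin. Nothing in the SAP suggests that cell would be chosen. This also stands.

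The 5% is a lenient baseline. The treatment-only model gives 5.8%, and the covariate model without borrowing gives 6.5 to 7.8%. Against no borrowing, the excess is clear for the low-risk reference (weak and moderate), the first- and last-listed genotype references, and the middle reference under strong effects. It is not clear elsewhere.

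The decision changes are not all due to the mismatch. With no covariate effects at all, 6.4% of decisions under the alternative and 4.3% under the null still differed between low- and high-risk references. That part comes from anchoring the prior on a single cell, so it is still dependence on coding.

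The mixture discounts conflict, and two analyses without the historical prior are planned. They would help to expose a problem, but they leave the primary rule undefined. Protocol 9.1 also lets the threshold rest on a desired confidence level instead of operating characteristics. However, Protocol 9.5 and SAP 5 both state a controlled 5%.

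**Conclusion.** The point holds and should be fixed. Under any reading of the prior, the SAP does not say what the intercept represents, and 92.7% and 5% are not shown for the model to be fitted. Under the readings that reproduce 92.7%, the choice of reference level can roughly double the stated 5% or, at one extreme reference, take power slightly below the 80% design claim (reading A; further below under B). If both mixture terms are variances, the coding has little effect, but the stated power is then not reproduced.

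The precision reading is an inference from the reproduction of 92.7%. The sizes rest on assumed covariate effects and covariate mix and should be read as illustrations. The false-positive effect is firmer than the power effect.

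**What to change.** In SAP 4.3.2, choose one of two specifications:

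- Place the mixture prior on the log odds of the covariate-standardised standard-arm rate. Standardise the Addendum 9 rate to the same covariate mix if the mixes differ. Under reading A this gives power of 94 to 96% and FPR of 5.2/6.0/5.0%.
- Centre the covariates at one fixed profile, and take the informative mean and standard error from the same covariate model fitted to the Addendum 9 standard-arm data. With heterozygote, middle tercile as the profile, power is about 90% and FPR 6.4/6.7/5.8%.

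Centring at sample means while keeping -1.48 is not enough (FPR 7.2/8.8/11.4%), because the log odds at average covariates is not the log odds of the average rate. In the moderate case it is -2.54 + 0.9 ln 2 + ln 1.3 + 0.2 ln 1.5 = -1.58.

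State the coding and reference levels, whether N(., .) takes a variance or a precision, and that p1 to p4 are averaged over the Safety Analysis Set. Rerun SAP 5 with the covariate model, including true standard-arm rates other than 18.5%. Apply the same to Week 52 and ARIA-H.

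The cost is SAP text, a simulation rerun and some programming; trial conduct does not change. The first option needs a custom log-density term with its Jacobian, and the second needs the four covariates in the Addendum 9 data. The restated figures may be slightly less favourable.

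The fix also restores full exposure to a wrong historical rate. These are FPRs under reading A with moderate effects, when the true standard-arm rate is not 18.5%:

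| True rate | Standardised-rate prior | Treatment-only model | Low-risk reference | No borrowing |
|---|---|---|---|---|
| 15% | 18.7% | 17.7% | 12.4% | 10.2% |
| 22% | 2.0% | 2.6% | 10.1% | 6.3% |

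The gains quoted for the two options assume that history matches the trial, which is why the rerun should include other rates.

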4.3.3. Sensitivity Analyses

One type of sensitivity analysis that will be conducted is to assess how a posterior probability described in (1), (2), or (3) in Section 2 will be changed if the margin or threshold is changed for relative risk reduction in ARIA-E. The calculated posterior probability regarding effect of interests will be computed.

One such analysis will be to compute a posterior probability of RD_{21} , RD_{31} , or RD_{41} being greater than 0. This is analogous to testing any positive relative risk reduction when a frequentist logistic regression was applied. Suppose from a posterior distribution of RD_{21} ,

$$Pr(RD_{21} > 0 \mid 24$$
-week ARIA-E data) > 0.8,

the conclusion would be compared to the standard dosing arm, the dosing skip arm had a significant positive relative risk reduction of ARIA-E.

Another type of sensitivity analysis will be to test how robust the yielded posterior probabilities will be if a neutral prior is assigned to the intercept coefficient rather than the mixture prior stated in Section 4.3.2.

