# 9.5. Sample Size Determination

Approximately 800 participants will be randomly assigned to 1 of 4 treatment arms in a 1:1:1:1 ratio. This sample size will provide over 80% power to demonstrate that there is more than 80% probability that at least one of the alternative regimens will reduce the ARIA-E rate by at least 20% compared to the standard regimen by 24 weeks.

The study power was calculated based on an assumed relative benefit of 40% reduction in ARIA-E rate by Week 24 in each of the alternative donanemab regimens compared to the standard regimen. In power calculation, the true ARIA-E rate by Week 24 in the standard donanemab regimen is assumed to be 18.5% and informative prior is elicited from the observed rate in historical data.

In the null scenario where all of the dosing regimens have the same true ARIA-E rate of 18.5% by Week 24, the probability that the CSF is met (i.e., the false positive rate) is controlled at 5% one-sided, or equivalently 10% two-sided.

The power and false-positive rate of the study were determined by simulation using R 4.1.2. Multiple virtual clinical studies were simulated under both null and alternative scenarios, and the Bayesian logistic model was fit in each dataset to obtain the operating characteristics.

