4.1. General Considerations

As 4 donanemab dosing regimens including the standard one are available for Study AACQ, any safety or biomarker analysis will involve 3 comparisons: 1) dose skipping vs. standard dosing; 2) titration vs. standard dosing; 3) Cmax (concentration maximum) vs. standard dosing.

Safety analyses will include subjects who are randomized to study treatment and who take at least 1 dose of treatment. Subjects will be analyzed according to the treatment arm to which they were assigned.

Unless otherwise specified, analyses for ARIA events are based on MRI findings or AE (adverse events) reporting. ARIA safety analyses will cover both ARIA-E and ARIA-H events by Week 24 as well as by Week 52. Bayesian logistic regression method is proposed to obtain a posterior distribution regarding relative risk reduction in ARIA-E or ARIA-H at Week 24 or 52 for each of 3 comparisons mentioned above. The details of logistic regression model, prior elicitation, and computation for the posterior distribution will be presented in Section 4.3.2. From each derived posterior distribution of RD_{21} , RD_{31} , and RD_{41} , summary statistics will be reported which include posterior mean, posterior median, posterior mode, a 2-sided equal-tailed 95% posterior interval (often cited as credible interval in Bayesian literature), and a posterior probability of achieving a minimum of 20% relative risk reduction in ARIA-E.

Frequentist methods will be used for the rest of the study objectives. All frequentist tests will be conducted at a 2-sided alpha level of 0.05; 2-sided confidence intervals (CIs) will be displayed with a 95% confidence level.

Unless otherwise noted baseline is defined as the last measurement prior to dosing. When change from baseline is assessed, subjects will only contribute to the analysis if both a baseline and a post-baseline measurement are available. Endpoint is the last non-missing post-baseline measurement within the time period for the given analysis.

To allow for evaluation of the primary and secondary hypotheses at 24 and 52 weeks, database locks and the assessments of corresponding primary and secondary objectives are expected to occur after all participants in the Safety Analysis Set have had the opportunity to complete visits 12 and 19 including PET and MRI assessments. The sponsor may choose not to have a separate database lock after visit 19 and wait to perform the analyses for 52-week data until the final database lock.

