The Bayesian power calculation was performed through simulations in both data generation and model fitting steps. In the data simulation stage, 1000 ARIA-E data sets were generated for every treatment arm. It was assumed that ARIA-E rate by Week 24 in the standard dosing regimen was 18.5% based on observations from AACI Addendum 9 data. In each alternative dosing regimen, ARIA-E rate was set to be equal to 11.1%, which translates to 40% relative risk reduction in ARIA-E compared to standard dosing regimen.

In the model fitting stage, a normal prior, N(0,4) was assigned to individual slope parameter of Arm 2, 3, and 4, respectively in the Bayesian logistic regression model. The intercept parameter was given a normal mixture prior, $0.5 \times N(-1.48, 4) + 0.5 \times N(-1.48, 30.19)$. The component prior mean (-1.48) in the mixture prior is equal to the natural log odds ratio of ARIA-E rate at 18.5% observed from historical study. For any simulated ARIA-E data with a complete sample size of 720, posterior samplers of RD_{21} , RD_{31} , and RD_{41} were simulated from 3 Markov chains with each chain composed of 10000 iterations after 10000 burn-ins. Among 1000 datasets generated, 927 satisfied at least one of the following probability statements:

```
Pr(RD_{21} \ge 0.2 \mid \text{simulated 24-week ARIA-E data}) > 0.8;

Pr(RD_{31} \ge 0.2 \mid \text{simulated 24-week ARIA-E data}) > 0.8;

Pr(RD_{41} \ge 0.2 \mid \text{simulated 24-week ARIA-E data}) > 0.8.
```

Hence, the reported power was 92.7% based on simulations.

In the null scenario where all the dosing regimens have the same true ARIA-E rate of 18.5% by Week 24, the false positive rate was controlled at 5% one-sided, or equivalently 10% two-sided.

The power and false-positive rate of the study were determined by simulations using R 4.1.2. Particularly, posterior samplers were generated through rjags package in R.

6. Supporting Documentation

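### SAP 4.3.3 calls an ARIA-E reduction significant when Pr(RD>0) exceeds 0.8, a rule met about one time in five per comparison when the arms do not differ

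*SAP*

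**What the plan says.** SAP Section 2 defines the relative reduction for each alternative arm as RD = 1 - p_k/p_1 and pairs a 20% margin with a 0.8 posterior threshold: "A posterior probability >80% will lead to a conclusion that at least 1 alternative dosing regimen reduces ARIA-E risk by at least 20" per cent against standard dosing. The false-positive statements go with that rule. Protocol 9.5 says that under equal rates "the probability that the CSF is met (i.e., the false positive rate) is controlled at 5% one-sided", and SAP Section 5 says "the false positive rate was controlled at 5% one-sided, or equivalently 10% two-sided".

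SAP 4.3.3 then varies the margin. It computes Pr(RD>0) for all three alternative arms and comments: "This is analogous to testing any positive relative risk reduction when a frequentist logistic regression was applied". Taking the dose-skipping arm as the example, it states that if this probability exceeds 0.8, "the conclusion would be compared to the standard dosing arm, the dosing skip arm had a significant positive relative risk reduction of ARIA-E". No error rate is given for this rule.

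The rule is reused. SAP 4.4.1 says "the sensitivity analyses proposed in Section 4.3.3 will be used for 52-week analysis of ARIA-E", and SAP 4.4.3 plans similar sensitivity analyses for ARIA-H. SAP 2.1 applies no multiplicity adjustment. SAP 4.1 sets frequentist tests at two-sided 0.05 and lists a 95% credible interval for each RD among the summaries to be reported.

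**The concern.** The 0.8 threshold is demanding only because of the 20% margin: the data must show a reduction well beyond 20% before 80% of the posterior lies above it. At margin zero with diffuse slope priors, the same threshold asks only for modest evidence of any reduction and behaves like a one-sided test at level 0.20. The SAP invites the comparison with a frequentist test and fixes the word *significant* in advance, while its frequentist tests elsewhere use two-sided 0.05.

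A reader who has seen the 5% statement would naturally carry it over to this conclusion. The study concerns a safety risk, so the practical stake is that a regimen could be reported as significantly lowering ARIA-E, at Week 24 or Week 52, on data that are also compatible with a sizeable increase.

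**Working it through.** **Inputs (SAP 4.3.3 and 5).** 720 evaluable participants over four arms, so 180 per arm. Null: 18.5% in every arm. Alternative: 18.5% against 11.1%. Priors: N(0, 4) for each arm slope; 0.5 N(-1.48, 4) + 0.5 N(-1.48, 30.19) for the intercept. Rule: Pr(RD>0) > 0.8.

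**Model.** logit p_1 = a, logit p_k = a + b_k, RD_k1 = 1 - p_k/p_1. Arm terms only, because the simulation described in SAP 5 names only the intercept and arm slopes. Posteriors were computed by numerical integration on a grid instead of MCMC, with 20,000 simulated trials for power and 60,000 for the null.

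**Prior notation.** The SAP does not say whether the second arguments are variances or precisions, so several readings were run. The value 30.19 looks like a precision: 30.19 / (0.185 x 0.815) = 200 participants' worth of information.

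**Reproducing the SAP's figure, then the label rate under the null (180 per arm).**

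| Prior reading | Power (stated 92.7%) | 20%-margin rule, per comparison | Pr(RD>0) > 0.8, per comparison | At least one of three |
|---|---|---|---|---|
| All variances | 84.7% | 3.2% | 19.8% | 39.2% |
| Slopes variance 4; mixture variance 4 and precision 30.19 | 92.7% | 2.1% | 19.9% | 44.5% |
| Slopes variance 4; both mixture terms precisions | 91.7% | 2.3% | 19.4% | 42.6% |
| All precisions | 73.7% | 0.8% | 16.4% | 39.9% |

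The second reading reproduces the stated power and the third comes close. With 200 per arm, the second reading gives 18.8% per comparison.

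**Check by hand.** With a near-flat slope prior, Pr(RD>0) is approximately Φ(z), where z is the estimated log odds difference over its standard error. Under the null z is standard normal, so Φ(z) > 0.8 has probability 0.20. For the 20% margin, the standard error of the log relative risk is sqrt(2 x 0.815 / (180 x 0.185)) = 0.221. The rule needs log RR below ln 0.8 - 0.842 x 0.221 = -0.223 - 0.186 = -0.409, that is z < -1.85, with probability 3.2%. Both values match the all-variance row.

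**Worked example.** 27/180 (15.0%) against 33/180 (18.3%), the other two arms also 33/180. Observed RD = 1 - 27/33 = 18%.

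- Log odds difference: ln(33/147) - ln(27/153) = 0.241.
- Standard error: sqrt(1/27 + 1/153 + 1/33 + 1/147) = 0.284.
- z = 0.847; one-sided p = 0.198; two-sided p = 0.40.
- Pr(RD>0) = 0.803 (all variances), 0.846 (power-reproducing), 0.819 (all precisions). All exceed 0.8.
- 95% credible interval for RD: -29% to +49% (all variances), -21% to +47% (power-reproducing).
- Pr(RD>=0.2) = 0.46, 0.47 and 0.38, so the primary rule fails clearly.

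**Dependence on the true rate.** Under the power-reproducing prior the intercept is drawn towards 18.5%, so a lower true rate makes the standard arm look worse than it is. The per-comparison label rate is 33% at a common true rate of 15% and 11% at 22%. These two rates are illustrative assumptions, not figures from the documents. Under the all-variance reading the rate stays near 20%.

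No rates were computed for Week 52 or ARIA-H, because the documents give neither event rates nor numerical priors for them.

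**The case against.** The strongest reply is that the SAP says what it means by *significant*. Its version history for version 2.0 adopts a posterior probability above 0.8 as the benchmark, and Protocol 9.1 lets the threshold be chosen for a desired confidence level instead of an error rate. A Bayesian analysis need not control type I error, and a one-in-five rate is simply what a 0.8 cut-off gives with a near-flat prior. The rule is also a sensitivity analysis, written out for one arm as an example, and decides nothing. The credible interval and Pr(RD>=0.2) are already listed for reporting, so a reader could see the weakness.

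Some of this stands. The primary criterion is untouched. The SAP makes no any-arm claim at margin zero, so the 39% to 45% figures are context and not the error rate of a stated rule. The remark in SAP 4.4.1 on "whether relative risk reduction of ARIA-E in 52 weeks is significant" introduces the main Week 52 model with its 20% margin and is not evidence of the margin-zero rule; only the later cross-reference to 4.3.3 is. The 33% and 11% figures depend on an inferred prior reading.

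The benchmark argument does not rescue the text. Section 2 ties 0.8 to the 20% margin, and Protocol 9.1 is about that primary criterion. In 4.3.3 the SAP itself draws the frequentist analogy, and the only error rate it quotes belongs to the other rule. Printing an interval beside the label does not make the label right.

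**Conclusion.** The concern holds. At the SAP's null, the margin-zero rule attaches *significant* to an arm with no benefit in about 20% of trials per comparison. That is roughly six to nine times the rate of the 20%-margin rule under the all-variance and power-reproducing readings (19.8/3.2 = 6.2; 19.9/2.1 = 9.5). The result rests on 180 evaluable per arm, a common rate of 18.5%, and a model without baseline covariates. The undefined prior notation does not change it: the only reading tried that falls clearly below one in five gives 16% and misses the stated power by 19 percentage points.

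This is a fault in a supportive conclusion and leaves the trial's success criterion as it is. It should be corrected because the wording is fixed in advance and is carried to Week 52 ARIA-E, and in similar form to ARIA-H.

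**What to change.** In SAP 4.3.3, report Pr(RD>0) for each alternative arm as a descriptive posterior probability together with its 95% credible interval. Delete the sentence that draws the significance conclusion, and drop or qualify the frequentist analogy. State that the 0.8 threshold applies only with the 20% margin. Carry the same wording to 4.4.1 and, where the analysis is reused, to 4.4.3.

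If a conclusion at margin zero is wanted, set its threshold by simulation over a range of true standard-arm rates and print the resulting false-positive rate. One cut-off tuned at 18.5% is not enough with the power-reproducing prior: 0.975 gives an any-arm error of 5.5% at 18.5% but 13.2% at 15%, and 0.98 gives 4.4% and 10.6%. Under the all-variance reading, 0.98 stays near 5% at 15%, 18.5% and 22%, so the SAP should also say which parameterisation its priors use.

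The cost is two or three sentences and a weaker supportive statement. Data collection, sample size and the primary analysis do not change. A calibrated rule would add simulation work.
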